9.4. Interim Analysis

The interim analysis serves to inform the Sponsor about the assumptions that underlie the trial procedures, endpoints, and sample size. The interim analysis will be performed after enrollment of approximately 50-60 subjects. The decision rules for increasing the sample size as well as the clinical and statistical considerations required for proper control and minimization of bias will be provided in the SAP.

ADMINISTRATIVE CONSIDERATIONS

10.1. Regulatory Considerations

This study will be conducted in accordance with the ethical principles that have their origin in the Declaration of Helsinki and that are consistent with GCPs and the applicable laws and regulations. The Investigator, head of the medical institution, or designee will promptly submit the protocol to applicable ethical review boards.

LB1148 is being studied in the U.S. under an IND application. Study sites will include approximately up to 15 sites in the United States.

All or some of the obligations of the Sponsor will be assigned to CRO(s).

10.2. Institutional Review Board or Independent Ethics Committee Approval

The study protocol and ICF, as well as any amendments, will be approved by the appropriate ethical review board (IRB or IEC) prior to initiation of the study at a particular site. All subjects will sign an ICF prior to any study-specific procedures. Site performance during the study will be routinely monitored by a study monitor (refer to [Section 10.7](#)).

Documentation of ethical review board approval of the protocol and ICF must be provided to the Sponsor *before* the study may begin at the study sites. The IRB/IEC will review the protocol and ICF as required in accordance with the ICH GCP guidelines. Any member of the IRB/IEC who is directly affiliated with this study as an Investigator or as site personnel must abstain from the vote on the approval of the protocol.

10.3. Subject Information and Consent

Written informed consent must be obtained from each subject or legal representative designee if subject is unable to sign after the nature of the study has been fully explained in accordance with ICH GCPs. Informed consent must be obtained prior to performing any study-specific procedures.

The subject (or surrogate) and the individual explaining the study will sign the current IRB/IEC-approved version of the consent form. A copy of the signed ICF will be given to the subject. The date that consent was obtained will be recorded on the eCRF as well as in the subject's chart.

A copy of the IRB/IEC approved version of the consent form will be provided to the Sponsor. The original signed consent form must be maintained at the site and made available for inspection, as appropriate.

10.4. Subject Confidentiality

The anonymity of subjects participating in this study must be maintained. Subjects will be identified by their assigned subject number in all written communications between the Investigator and Sponsor or its designees. Site documents that are not submitted to the Sponsor or its designees and that identify the subject (e.g., signed informed consent; source documents/charts) will be made available to the Sponsor (or its designees) or regulatory authorities for inspections, but will be maintained in confidence.

All study-related information provided by the Sponsor or its designees to the Investigator and not previously published, including but not limited to the active study agent identity, the Investigator's Brochure, the study protocol, verbal and written communication, study data, assay methods and scientific data, will be considered confidential. In addition, all information developed during the conduct of the clinical investigation of the study agent is also considered confidential. Neither the Investigator nor any of his/her employees or agents shall disclose or use this information for any purpose other than the performance of the clinical study. Such information shall remain the confidential and proprietary property of the Sponsor, and disclosure to others will be limited to other physicians who are conducting studies with the same active study agent, the IRB/IEC, and the applicable regulatory authorities except by prior written permission of the Sponsor or its agents. At such time, that information becomes widely and publicly available through no fault of the Investigator, the obligation of nondisclosure toward that particular information will cease.

10.5. Case Report Forms and Study Records

Data collected through the completion of study procedures required by this protocol will be recorded in the subject's chart as source documentation. This data will then be transcribed onto the appropriate eCRFs.

All information in the eCRFs must be supported by original data in the subject's medical records. All medical records, laboratory printouts, notes made by the physician, and other materials will be considered source data and must be available for inspection by the Sponsor, the Sponsor's designees, or governmental representatives.

Appropriate site personnel training will occur prior to subject enrollment for the study. The Investigator remains responsible for the accuracy and adequacy of all study data.

Study data will be monitored as described in [Section 10.6](#) and [Section 10.7](#).

Upon further data processing, queries may be generated and sent to the Investigator for clarification or correction. The Investigator and/or delegated site personnel will address any queries and forward resolutions as directed by the site monitor.

10.6. Safety Monitoring

The Sponsor or their designated Medical Monitor will review blinded safety data throughout the course of the study. All SAEs will be reviewed within time frames mandated by company procedures and local regulatory requirements. The Sponsor or their designee will review safety trends and laboratory analytes at periodic intervals.

All deaths and SAE reports will be reviewed in a blinded manner by the Sponsor or its designee(s) during the study. These reports will be reviewed to assure completeness and accuracy, but will not be unblinded to the clinical team during the study. If a death or clinical AE is deemed serious, unexpected, and possibly related to study drug (refer to [Section 0](#)), only the Sponsor or its designees will be unblinded for regulatory reporting and safety monitoring purposes (refer to [Section 5.5](#)). The clinical site will have the ability to do an emergency code break on an individual subject at their site. These measures will preserve the integrity of the data collected during this study and minimize any potential for bias while providing for appropriate safety monitoring.

10.7. Protocol Deviations

Sites are responsible for abiding by their IRB rules and regulations for reporting protocol deviations. Additionally, the following important protocol deviations will be reported to the Sponsor:

- Subject did not meet study eligibility criteria
- Subject did not receive the correct treatment assignment
- Subject received the wrong amount of a dose IP (i.e., $\pm 20\%$ of assigned dose)
- Subject received a prohibited concomitant medication
- Subject was not assessed for intra-abdominal adhesions

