6.16. Adhesions Assessment (Day 0 and at time of second surgery)

The surgeon will determine the incidence, extent, and severity of adhesions at the time of surgical closure for the first surgery and at the time of opening for the second surgery. Grading of the adhesions (extent and severity) will be performed by the surgeon during the surgical procedure ([Appendix 5](#)).

For each abdominal region, the score of the extent and severity of adhesions are evaluated. The surgeon will grade the intra-abdominal adhesions at 9 abdominal region (right upper, epigastrium, left upper, left flank, left lower, pelvis, right lower, right flank and central) and when appropriate at 4 areas around the ostomy (superior, lateral, inferior, and medial). ([Coccolini et al., 2013](#), [Dabrowski et al., 2016](#), and the [Seprafilm Package Insert](#)).

For each abdominal region, extent of adhesion formation is scored for adhesions from the abdominal wall to bowel (including abdominal wall to viscera) and for adhesions from bowel to bowel (including bowel to viscera) as follows:

- 0 = no adhesion;
- 1 = minimal (<1/3 of the site is covered);
- 2 = moderate (1/3 to 2/3 of the site is covered), or
- 3 = extensive (>2/3 of the site is covered).

The severity of the adhesions in the region are graded using the following score:

- 0 = no adhesions;
- 1 = filmy thickness, avascular;
- 2 = moderate thickness, limited vascularity, or
- 3 = dense thickness, vascularized.

At the second surgery visit the site study staff will determine if the subject experienced a hospital readmission due to GI concerns and/or other medical reasons. If readmission did occur, this event should be recorded as a SAE.

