Appendix 1 Schedule of Assessments Protocol LBS-POI-201

Study Day	Screening	Surgical	Post-Surgical				Follow-Up	Second Surgery
	(-42 to -1 Days) ^{1,2}	Pre-Surgery / Surgery Day 0 ²	Post-Operative Days 1-6 ³	Post-Operative Day 7 ³	Post-Operative Days 8-14 ³	Hospital Discharge (Early Termination)	Day 30 (+7 Days)	Up to 8 Months after Day 0
Informed Consent	X							
Surgery Assessment		X						X
Study Eligibility Assessment ⁴	X	X ⁵						
Demographics & Medical History ⁵	X	X						
Concomitant Medication and Blood Products Review ^{5,6}	X	X	X	X	X	X		
Randomization ¹	X	X						
Taste Assessment		X						
Physical Exam ⁷	X	X	X	X	X	X		
Vital Signs ⁸	X	X	X	X	X	X		X
Study Drug Administration ^{2,9,10}	X	X						
Perioperative Surgical Preparation ¹¹	X	X						
Record Opioid Use	X	X	X	X	X	X		
Pain Assessment		X	X	X	X	X		X

Study Day	Screening	Surgical	Post-Surgical				Follow-Up	Second Surgery
	(-42 to -1 Days) ^{1,2}	Pre-Surgery / Surgery Day 0 ²	Post-Operative Days 1-6 ³	Post-Operative Day 7 ³	Post-Operative Days 8-14 ³	Hospital Discharge (Early Termination)	Day 30 (+7 Days)	Up to 8 Months after Day 0
GI Function Assessment								
Nausea			X	X	X	X		
Vomiting or Retching			X	X	X	X		
Flatus ¹²			X	X	X	X		
Stools ¹²			X	X	X	X		
NG/OG Tube			X	X	X	X		
Liquid Diet ¹²			X	X	X	X		
Solid Diet ¹²			X	X	X	X		
Adhesions Count		X						X
Hospital Discharge								
Hospital Discharge Order Written			X	X	X	X		
Hospital Departure			X	X	X	X		
Subject's Willingness To Discharge			X	X	X	X		
Adverse Events (AE)	X	X	X	X	X	X	X ¹³	X ¹⁴
Local Laboratory Tests¹⁵								
Urine or Serum Pregnancy Test ^{4,5}	X	X						
Labs (CBC, coagulation, and metabolic) ¹⁵	X		X	X				

Abbreviations: GI = gastrointestinal.

¹ Screening and Day 0 (Pre-Operative/Pre-Surgery) can be combined if the visit is on the day of first surgery. If this is the case, randomization will be performed during this study visit.

² Study Day 0 starts on the calendar day of the surgery; study dosing could occur Day -1 and/or up to 2 hours prior to surgery on Day 0.

³ Subject will be monitored from Screening through Post-Operative Days 14 until Hospital Discharge or Study Termination (whichever occurs first).

⁴ Eligibility assessment will include, if applicable, a negative pregnancy test.

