4 GENERAL METHODS

4.1 Analysis Populations

Due to coronavirus disease 2019 (COVID-19), some subjects enrolled and randomized prior to 01Jan2022 were released from the hospital prior to achieving GI2. In addition, subjects were randomized based on whether the surgery was to include a stoma or not and a subject was considered completed at Study Day 30, e.g., the second surgery was optional. Protocol Amendment 5 and 6 require subjects to have a stoma during the first surgery and require the second surgery for the subjects to be considered complete. The primary endpoint is now comparing the change from baseline in extent and severity of intra-abdominal adhesions rather than GI2 among subjects treated with LB1148 or placebo. These circumstances and changes require corresponding updates to the populations defined in the Study Protocol.

The **modified Intent-to-Treat (mITT)** population includes all randomized subjects who received any investigational test article on or after 01Jan2022, where subjects will be analyzed according to the treatment to which they were randomized.

Safety Population: The safety population will be defined as all subjects who receive any amount of investigational test article. Subjects will be analyzed according to the treatment actually received.

The **Per Protocol Population (PP)** includes subjects in the mITT population who met all inclusion and no exclusion criteria, received the complete appropriate study dose, and had no important protocol deviations or violations, where subjects will be analyzed according to the treatment to which they were randomized.

Study subjects may be replaced if found to be ineligible (violation of one or more inclusion/exclusion criteria), or if following randomization, did not go on to receive ANY amount of investigational test article.

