Selected time-to-event secondary efficacy endpoints (See Table in Section 11.5) will be analyzed using a stratified Cox PH model with treatment as the main effect, stratified by surgery type (laparotomy versus minimally invasive). In addition to surgery type, a categorical age (<65 years, ≥ 65 years) will be included. Nominal p-values will be reported. Comparison of treatment groups and assessment of the significance of the parameter estimates for surgery type will be made using the Wald chi-square test.

In addition to the semi-parametric Cox PH model, non-parametric Kaplan-Meier survival curves will be produced for the two treatment groups and compared using a stratified log-rank test; results from this test will be considered nominal/hypothesis-generating in nature. The number of hours to each endpoint will be presented in summary tables with descriptive statistics for the mITT (all variables selected) and PP populations (POI, GI2, and GI3 variables only).

Those endpoints defined as yes/no variables will be analyzed using a chi-square test for homogeneity of proportions.

All findings will be presented in subject listings for the mITT population, including calculated time to event efficacy variables.

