11.5 Efficacy Time-to-Event Parameter by Analysis Type

Number of hours to Analysis	Cox PH		Kaplan-Meier		Other	
	mITT	PP	mITT	PP	mITT	PP
GI2	Yes	Yes	Yes	Yes	Frequency Table	Frequency Table
Bowel movement within 14 days	Yes	No	Yes	No	Frequency Table	No
NG/OG use (insertion, reinsertion)	No	No	No	No	Frequency Table only	No
NG/OG removal	No	No	No	No	Listing only	No
Liquid oral diet	No	No	Yes	No	Frequency Table	No
Solid oral diet	Yes	No	Yes	No	Frequency Table	No
GI3	Yes	Yes	Yes	Yes	Frequency Table	Frequency Table
POI within 14 days	Yes	Yes	Yes	Yes	Frequency Table	Frequency Table

Number of hours to Analysis	Cox PH		Kaplan-Meier		Other	
POI after discharge	No	No	No	No	Included in Frequency Table for POI within 14 days	No
Discharge order written	Yes	Yes	Yes	Yes	No separate descriptive Frequency Table	No separate descriptive Frequency Table
Actual discharge	Yes	Yes	Yes	Yes	No separate descriptive Frequency Table	No separate descriptive Frequency Table
Standard discharge	No	No	No	No	Listing only	No
Nausea	No	No	No	No	Listing only	No
Vomiting	No	No	No	No	Listing only	No
Flatus	No	No	No	No	Listing only	No

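### The single per-protocol set lets a missing second-surgery adhesion assessment, up to 8 months later, remove subjects from the 14-day bowel-function, POI and discharge analyses

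*Protocol*

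**What the plan says.** **PP definition.** SAP 4.1 has one PP set: mITT subjects who met the entry criteria, "received the complete appropriate study dose, and had no important protocol deviations or violations". It is not endpoint-specific.

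**Deviation list.** Protocol 10.7 says "the following important protocol deviations will be reported to the Sponsor" and gives five items. Four concern eligibility, treatment assignment, amount of dose and prohibited medication. The fifth is "Subject was not assessed for intra-abdominal adhesions". It names neither surgery and has no time limit.

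**Timing of the assessment.** Protocol 6.16 schedules adhesion scoring "at the time of surgical closure for the first surgery and at the time of opening for the second surgery". The Schedule of Assessments places the second surgery "Up to 8 Months after Day 0", and Protocol 3.1 allows a later date with Medical Monitor approval. SAP 4.1 says that Amendments 5 and 6 "require the second surgery for the subjects to be considered complete".

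**Where PP is used.** SAP 11.2.2 summarises hours to event for "PP populations (POI, GI2, and GI3 variables only". SAP 11.3 adds PP summaries for length of stay. The table in SAP 11.5 marks PP as Yes, for both Cox and Kaplan-Meier, for GI2, GI3, "POI within 14 days", discharge order written and actual discharge. SAP 11.4 censors GI2, GI3 and both discharge endpoints at Study Day 14.

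**The concern.** Read together, these sections let an event months after the first operation decide who enters an analysis of the first 14 days. A subject whose bowel-function, POI and discharge data are complete can be removed because a later adhesion assessment is missing, and that assessment contributes nothing to those endpoints.

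Two things are at stake. One is precision, in a trial that expects only about 30 randomized subjects for its current purpose. The other is validity. If reaching the second surgery is related to early recovery, complications or treatment, the PP estimates for the 14-day endpoints are conditioned on a consequence of the outcome. A difference between PP and mITT could then reflect this selection and not adherence to the treatment plan, and agreement between them would be equally hard to interpret.

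**Working it through.** The plan states no power, alpha or sample-size figure that depends on this rule, so there is no figure to reproduce. The check is a trace of the definitions, followed by an illustration with assumed rates.

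**Step 1: the chain of definitions.**
- SAP 4.1 excludes subjects with important protocol deviations from PP.
- Protocol 10.7 is the only list in either document under that term, and a missing adhesion assessment is on it.
- The second assessment is due up to 8 months after Day 0.
- SAP 11.2.2, 11.3 and 11.5 use the same PP set for endpoints observed over 14 days.
- Neither document confines the adhesion deviation to the adhesion endpoints or defines a second PP set.

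A missed assessment at the first surgery would also count as the deviation, but it precedes the outcomes. The post-outcome selection comes only from the second assessment.

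**Step 2: conflict with the censoring rules.** SAP 11.4 keeps subjects who die, are lost or withdraw without reaching the event, and censors them at Study Day 14. Those subjects can have no second-surgery assessment. Unless such cases are exempt from the deviation, which neither document says, PP removes subjects whom the censoring table is written to keep.

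**Step 3: size of the set.** Take N = 30 from SAP 4.3, assuming all 30 are dosed and so in mITT, and let m be the assumed proportion with no second assessment. The number left on this ground alone is N × (1 − m).
- m = 10%: 30 × 0.90 = 27
- m = 20%: 30 × 0.80 = 24
- m = 30%: 30 × 0.70 = 21

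**Step 4: effect on an estimate.** Let p be the true POI rate, and let a and b be the probabilities of having no second assessment with and without POI. Then

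PP rate = p(1 − a) / [p(1 − a) + (1 − p)(1 − b)].

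Every rate below is an assumption.

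| Scenario | Placebo in PP | Active in PP | Difference |
|---|---|---|---|
| True 30% vs 15%; a = b = 25% | 30.0% | 15.0% | 15.0 points (unbiased) |
| True 30% vs 15%; a = 40%, b = 15% in both arms | 23.2% | 11.1% | 12.1 points |
| True 30% vs 15%; a = 50%, b = 10% in both arms | 19.2% | 8.9% | 10.3 points |
| No effect, 30% in both; b = 15%; a = 20% placebo, 40% active | 28.7% | 23.2% | 5.5 points (spurious) |
| No effect, 30% in both; b = 15%; a = 10% placebo, 50% active | 31.2% | 20.1% | 11.1 points (spurious) |

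For example, the placebo figure in the second row is 0.30 × 0.60 / (0.30 × 0.60 + 0.70 × 0.85) = 0.180 / 0.775 = 23.2%.

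When loss is unrelated to POI (first row), the rates do not change and only precision is lost. When it depends on POI equally in both arms, the difference shrinks in these examples. When the dependence differs by arm, a difference can appear where none exists. Swapping the arms in the last two rows would reverse its sign.

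**The case against.** **The link is an inference.** The SAP does not cite Protocol 10.7, and that section lists deviations for reporting to the sponsor, not for defining analysis sets. Its adhesion item could mean that surgery took place without scoring, and not that a takedown never happened. This stands as a limit on certainty. But no other list of important deviations exists, and on either meaning a missing second assessment removes a subject from the 14-day PP analyses.

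**The consequence is limited.** SAP 4.2 analyses all efficacy endpoints in mITT, uses PP as an additional set, treats p-values as nominal and makes no multiplicity adjustment. SAP 11.3 treats length of stay as exploratory. This stands and limits the severity.

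**Stronger readings that the documents do not support.**
- A reader might take the step from 40 to 30 subjects in SAP 4.3 as a 25% loss of second assessments, with standard errors rising by about 15% (1/√0.75 = 1.155). That step is from enrolled to randomized subjects. Those lost there never enter mITT, so they cannot be lost from PP. The standard-error figure also assumes that precision scales with the number of subjects, whereas in Cox and Kaplan-Meier analyses it depends mainly on events.
- A reader might infer that subjects with a difficult recovery are removed preferentially. That is plausible, but the documents give no data on it. Slow recovery need not mean a missed assessment, since the window can be extended. The reason that the amendment summary gives for the 8-month period is recovery from cancer treatment, not early bowel function.

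**Conclusion.** The point holds, with moderate impact. As written, the plan can exclude subjects with complete 14-day data from the PP analyses of GI2, GI3, POI and discharge because of a missing assessment up to 8 months later. This rests on reading the SAP's exclusion term as the list in Protocol 10.7.

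The rate of missed second assessments is not given, so the reduction from 30 to between 27 and 21 rests on an assumed 10% to 30%. Bias is conditional: it needs reaching the second surgery to depend on early recovery, complications or treatment, and the documents fix neither its presence nor its direction. The mITT results for these endpoints are unaffected.

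**What to change.** State the following in SAP 4.1, before database lock and unblinding:

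- A missing second-surgery adhesion assessment excludes a subject from PP for the adhesion endpoints only.
- PP for the 14-day endpoints (GI2, GI3, POI within 14 days, discharge order written, actual discharge) is based on eligibility, complete dosing and important deviations up to Day 14.
- The list of important deviations meant in the PP definition is the one in Protocol 10.7, if that is the intention, or another that is then given. The text should also say whether an assessment missed through death or withdrawal counts.

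The cost is a short addition to the SAP and one extra population flag. No new data are needed. The change-from-baseline adhesion analysis loses nothing, because SAP 4.4.1 does not impute missing scores and a subject without the second assessment cannot contribute to it in any case.

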10.8. Study Monitoring and Access to Source Documentation

To ensure the safety of participants in the study, and to ensure accurate, complete, and reliable data, the Investigator will keep records of laboratory tests, clinical notes, and subject medical records in the subject files as original source documents for the study. If requested, the Investigator will provide the Sponsor, applicable regulatory agencies, and applicable ethical review boards with direct access to original source documents.

The Sponsor or its designees (e.g., CRO) will assure the accuracy of data, the selection of qualified Investigators, appropriate study centers, and review protocol procedures with the Investigators and associated personnel prior to the study and during periodic monitoring visits. The Sponsor or its designee will review study data for accuracy and completeness during monitoring visits. Discrepancies will be resolved with the Investigator as appropriate.

The Sponsor or its designees will monitor the study using any of the following methods:

- Frequent telephone contacts;
- Email;
- Periodic site visits;
- Review of original subject records, eCRFs, study drug accountability, and
- Storage, and general study documentation.

So that the study may be adequately monitored, the Investigator or delegated site personnel will cooperate in providing the Sponsor or its designees with all study documents (e.g., subject charts and study files) and responding to inquiries that may arise as a result of the document review.

Review of these documents will usually occur during a routine monitoring visit, but may also be required during a visit by a quality assurance auditor. The Sponsor reserves the right to terminate the study if access to source documentation is denied to the Sponsor or quality assurance representatives.

